Defining V2V Engagement level: Engagement measures include: Number of intervention assessments completed, peer videos viewed, and peer coaching interactions. To assess each of these, we will first categorize an adolescent's engagement with each component. For example, for intervention assessments, we will calculate percent of assessments completed (number of assessments divided by the total number of assessment opportunities). Second, we will then calculate the median percent complete across the sample and dichotomize into higher engaged (adolescent's percent completed was at the median or higher) or lower engaged (under the median). We will use a similar procedure for the peer videos viewed. Third, for peer coaching, we will use the count of the number of messages to the peer coach. We anticipate that this count could vary considerably, as some will have sent 0 messages and there is no absolute maximum number of messages sent. We will base the higher versus lower engaged based on the distribution (median split or another reasonable quantile). We could then look at the distribution of engagement with each component, and predictors of engagement (by the adolescent's characteristics).

From these three measures, we will create an *engagement summary score*. The range for the summary score would be from 0 to 3 (0 = lower engagement in all 3 measures, 3 = higher engagement in all 3). We will assess the association of this score with the acceptability and satisfaction score using linear mixed modeling. Acceptability and satisfaction scores will be calculated using the Client Satisfaction Questionnaire (CSQ-8). The overall score is calculated by summing the respondent's rating (item rating) score for each scale item. Scores therefore range from 8 to 32, with higher values indicating higher satisfaction. Similarly, we will look for association between summary score and cessation. We recognize that, for these analyses, power will be limited due to the sample, and further we do not have estimates upon which to base estimates for power calculations. These analyses are conducted to guide our future R01.

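### The 0–3 engagement score, the only stated engagement predictor of CSQ-8 and cessation, discards information by dichotomising, and its cut rules do not cover a median of zero

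*Combined protocol and SAP*

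**What the plan says.** Section 13, under the heading on defining engagement level, treats the three components as follows.

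- **Intervention assessments (texting quizzes).** Percent completed is cut at the sample median: "we will then calculate the median percent complete across the sample and dichotomize into higher engaged" and lower engaged, with the dividing rule worded as "percent completed was at the median or higher) or lower engaged (under the median". Ties at the median therefore count as higher.
- **Peer videos.** "We will use a similar procedure for the peer videos viewed".
- **Peer coaching messages.** No cut is fixed. The plan expects that "some will have sent 0 messages and there is no absolute maximum number of messages sent", and lets the split be a "median split or another reasonable quantile", based on the distribution.

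The three splits are added to give a score from 0 to 3, which is then related to CSQ-8 and, similarly, to cessation. Looking at the components one by one is mentioned as a possibility, for their distributions and predictors but not against CSQ-8 or cessation. Under Aim 2C engagement is also listed as a possible mediator, without saying in what form. The plan concedes limited power and says these analyses are meant to guide a future trial. Table 2 shows that engagement is recorded in the V2V arm only.

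**The concern.** Two separate problems arise.

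First, splitting a graded measure treats a student just above the median like the heaviest user, and a student just below it like a non-user. Three such splits leave a predictor with four values. In about 34 students that is an avoidable loss.

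Second, a rule that counts values at the median as higher breaks down when the median is the lowest possible value. Everyone then qualifies, non-users included, and the component adds a constant 1. For assessments and videos the rule is fixed, with no provision for this case. For coaching, the one component where zeros are foreseen, the cut is left until the data are visible. A workable cut can be chosen, but nothing requires it, and different permitted cuts give different scores.

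Aim 2B is a named aim, and its engagement results are intended to inform the next study.

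**Working it through.** **Inputs from the documents.** 40 students per condition; 85% retention, giving 40 × 0.85 = 34 per condition at 6 months (Section 25). CSQ-8 is collected at 6 months only (Table 2), so the association has about 34 students.

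**The plan's own figures.** None is given for the engagement analysis. The sample-size figures that are given reproduce: design effect 1 + 0.01 × 19 = 1.19; 40/1.19 = 33.6, rounded to 34; exact 95% interval for 29/34 = 68.9% to 95.0%.

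**Step 1: information lost by splitting.** For one normally distributed predictor, a median split keeps 2/π = 0.64 of the efficiency, so 34 students act like 34 × 0.637 ≈ 22. Summing three splits recovers part of this, so the score itself was simulated.

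Assumptions, none of them in the documents: three normal components with pairwise correlation 0.4; an outcome correlated with their sum; n = 34; a correlation test at two-sided 0.05; no school clustering. The comparator is the mean of the three components' ranks.

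| Assumed true correlation | Power, 0–3 score | Power, mean rank | Difference (points) |
|---|---|---|---|
| 0.2 | 0.17 | 0.20 | 3 |
| 0.3 | 0.32 | 0.41 | 9 |
| 0.4 | 0.53 | 0.64 | 11 |
| 0.5 | 0.75 | 0.86 | 11 |
| 0.6 | 0.91 | 0.97 | 6 |

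Repeat runs move these figures by about 0.01. With inter-component correlation varied from 0.2 to 0.5, and the plain continuous sum as comparator, power at a true correlation of 0.4 is 0.50 to 0.54 for the 0–3 score against about 0.67. At n = 40 it is 0.58 to 0.61 against about 0.74.

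**Step 2: zero median under the fixed rule (assessments, videos).** Apply the at-or-above rule to n students with k zeros:

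| n | Zeros | Median | Higher, at or above | Higher, strictly above |
|---|---|---|---|---|
| 34 | 17 | between 0 and the next value | 17 | 17 |
| 34 | 18 | 0 | 34 | 16 |
| 40 | 20 | between 0 and the next value | 20 | 20 |
| 40 | 21 | 0 | 40 | 19 |

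The failure needs more than half at zero. Once it happens, the score can no longer be 0 and its range shrinks to 1–3.

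**Step 3: the open coaching cut.** Suppose 24 of 40 students send no messages and the other 16 send differing numbers. Counting values at or above the cut as higher:

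- 25th or 50th percentile: all 40 are higher.
- 60th, 67th or 75th percentile: 16, 13 or 10 are higher.

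All of the upper cuts, and the median, fit the plan's wording.

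**The case against.** The strongest reply is that this is exploratory work whose low power is admitted, that raw counts are collected so nothing is irretrievably lost, and that H1 and the retention-based sample size do not depend on it. All of that stands and limits the weight of the point. It does not answer why a weaker predictor should be the only one planned when a better one uses the same data.

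A second reply is that the size of the loss is assumed. This is right: the plan says it has no estimates for power calculations, the videos number only 8–10, and coaching is a count, so normality is a convenience. The 0–3 score had lower power at every correlation tried, but the gap ranges from 3 to 11 points.

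Four stronger readings are tempting, and the documents do not support them.

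- *All three components are cut at the median, so coaching will degenerate.* The coaching cut may be another quantile, and Step 3 shows that such a cut avoids the problem. The gap is that nothing rules out a median of zero.
- *Many students will have zero assessments or videos.* Nothing in the documents says so; that failure is conditional.
- *Half at zero is enough.* With 34 or 40 students and exactly half at zero, the split works.
- *The mixed model has a school variance resting on one degree of freedom.* The plan says only "using linear mixed modeling" for the CSQ-8 association and names no random effect there. Section 6 allows 4–7 schools, so exactly two V2V schools cannot be assumed.

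**Conclusion.** The point holds as a minor one. The information loss follows from the construction of the score. Its size, about 3 to 11 points of power at 34 students over assumed correlations of 0.2 to 0.6, rests on the normality, correlation and significance-level assumptions above. It was worked out for a continuous outcome such as CSQ-8; the cessation association was not simulated.

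The zero-median failure is certain if 18 of 34 (or 21 of 40) students are at zero on assessments or videos, but whether that will occur is unknown. The coaching cut is unspecified as the plan stands. Recruitment, retention and the sample-size justification are untouched.

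**What to change.** In the Aim 2B text of Section 13:

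1. Make a continuous engagement summary the predictor of CSQ-8 and cessation, for example the mean of the three components' percentile ranks, with tied students sharing the average rank.
2. Keep the 0–3 score for description only.
3. For that description, count a student as higher only if strictly above the median whenever the median is zero.
4. Set the coaching cut before the data are seen, for example any messages against none.

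The cost is one paragraph of wording and no new data. The small downside is a summary that is less simple to describe than a count from 0 to 3.

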6. INCLUSION AND EXCLUSION CRITERIA*

Aim 1 Study Population (20 adolescent e-cigarette users (Peer Advisory Panel) and two key informants)

The study population will be derived from 20 adolescent e-cigarette users in one high school selected for its high rate of racial/ethnic minorities and low SES status. We will also recruit two key informants (school nurse and Vice Principal) from the same high school.

Inclusion criteria for peer advisory panel: (1) enrolled in grade 9-12 at a local high school; (2) current e-cigarette user; (3) have a smartphone; and (4) English- or Spanish-speaking. Current e-cigarette user is defined as a response greater than “0 days” to the question: “During the past 90 days, on how many days did you use e-cigarettes?” This eligibility criterion is modeled on a question in the 2018 National Youth Tobacco Survey (NYTS), a survey of U.S. middle and high school students which used a 30-day timeframe.

Exclusion criteria for peer advisory panel: (1) unable or unwilling to provide informed assent or consent (in the case of those aged 18 years or older).

Inclusion criteria for two key informants: (1) employed as a school nurse or Vice Principal at the Aim 1 high school.

Exclusion criteria for two key informants: (1) unable or unwilling to participate in the study.

Aim 2 (80 adolescent e-cigarette users and up to 12 key informants)

In Year 2 of the project, 80 adolescent e-cigarette users in 4-7 high schools selected for their high rates of racial/ethnic minorities and low SES status (20/school, 40/study condition) will be recruited and complete assessments at baseline and 6-month follow-up.

Inclusion criteria for 80 adolescent e-cigarette users: (1) enrolled in grade 9-12 at a participating high school; (2) current e-cigarette user; (3) have a smartphone; and (4) English- or Spanish-speaking. Current e-cigarette use is defined as a response greater than “0 days” to the question: “During the past 90 days, on how many days did you use e-cigarettes?” This eligibility criterion is modeled on a question in the 2018 National Youth Tobacco Survey (NYTS), a survey of U.S. middle and high school students which used a 30-day timeframe.

Exclusion criteria for 80 adolescent e-cigarette users: (1) unable or unwilling to provide informed assent or consent (in the case of those aged 18 years or older).

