With participant permission, we will collect complete and accurate contact information from the student at baseline, including home address, phone, cell phone, email, and phone numbers of three contacts and best times and days to reach them to maximize retention. A contact sheet will be completed by the participant that will include the above information. Care will be taken to maintain the confidentiality of the student's participation; therefore all students will be asked to provide us with the individuals or contact information where they feel comfortable being contacted by study staff or where they feel assured that the confidentiality of their participation will be maintained. The other contacts provided by the student will not be informed of the student's vaping status. We have found in prior studies that cell phone numbers and e-mail addresses are particularly helpful in remaining in contact with this population. Tracking procedures will be implemented for any student who does not attend a scheduled study visit or who is not accessible by telephone or e-mail at the contact location provided. Attempts to locate students will be made mainly through the schools and by telephone calls to the contacts provided or directory assistance.

Table 2. Study Assessments, Measures and Data Collection Timing

Variable and Measure	Relevant Aim	Baseline	6-month follow-up
Recruitment: # screened and eligible, # and reasons for refusal	2A	•	
Retention: # of dropouts, reasons for dropping out	2A		•
Engagement (V2V only): # of completed responses to texting quizzes, peer videos viewed, peer coaching interactions	2B		*
Acceptability and satisfaction: Client Satisfaction Questionnaire (CSQ-8) semi-structured interview	2B		•
Cotinine-validated 7-day point prevalence abstinence: saliva samples collected from all; analyzed for those reporting 7-day abstinence; cut-off 11.4 ng/ml	2C		•
E-cigarette use frequency (past 7 and 30 day) and intensity (# days and amount vaped in past 7 and 30 day)	2C	•	•
THC/marijuana and other tobacco use frequency (past 7 and 30 day) and intensity (# days and amount vaped)		•	•
Social Cognitive Theory (SCT) constructs			
Self-efficacy, confidence to quit: Self-efficacy Questionnaire (SEQ-12)		•	•
Demographics and tobacco use			
Demographics: age, gender, socio-economic status, race/ethnicity, grade in school, academic performance		•	•
History of all tobacco use, past and recent quit attempts, cessation strategies used		•	

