Attitudes about e-cigarette and other tobacco use		•	•
Stage of change: Prochaska's Stages of Change		•	•
Severity of nicotine addiction: Hooked on Nicotine Checklist (HONC) (adapted for vaping)		•	•

Semi-Structured Interviews: In addition to the above assessments, we will conduct brief qualitative interviews with all intervention participants after they have completed six-month follow-up to deepen our understanding of their experience with the V2V program and obtain

specific feedback on ways to improve the program for future refinements. The interviews will examine a series of topics, including constructs from our hypothesized conceptual model, as well as participant perceptions of each of the V2V components, message content, and system usability. Across these topics, our goal will be to understand what participants most valued and to elicit recommendations for further intervention enhancement. Interviews will be semi-structured, allowing for natural conversation with opportunities to explore unanticipated issues. We anticipate interviews to be no more than 60 minutes in duration. The interview guides will be submitted to the IRB for review and approval prior to use in the study.

Compensation: Gift cards worth \$25 will be provided to adolescents for completion of each assessment (baseline and 6-months; \$50 total).

Key Informant Recruitment and Enrollment:

Recruitment of eight key informants (school nurse, Vice Principal, or other academic administrator) will take place in-person at the high school. We are requesting a waiver of document of consent for the key informants. We will provide key informants with a fact sheet.

Semi-Structured Interviews with Adult Key informants: We will employ semi-structured individual interviews with the school nurse, vice principal, or other academic administrator (minimum of 2 key informants) from each participating high school. We will develop two complementary interview guides, one for adolescents and one for adult key informants. The interview guides will be submitted to the IRB for review and approval prior to use in the study. The semi-structured interview is expected to last no more than 60 minutes.

Compensation: Gift cards of \$100 will also be provided to the key informants (school nurse, Vice Principal, or other academic administrator).

See also #30, *Consent Process* and #9, *Study Timelines*.

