Aim 2A (Feasibility) Hypothesis H1: *We will be able to recruit 80 adolescents (20/school, 40 per study condition), and $\geq 85\%$ will be retained in each study condition at 6-month follow-up.* We will estimate recruitment rates, overall and per condition. Also, for each condition, we will model 6-month retention, using generalized estimating equation (GEE) logistic regression to account for within-school clustering and dependence over time.

Proposed Sample Size. As appropriate for a pilot study, we are estimating our power and sample size based on the feasibility hypothesis (H1). Because pilot studies do not provide meaningful estimates of effect sizes due to the imprecision inherent in small samples, we base our proposed sample size of 40 students per condition (20 per school) on obtaining precision in estimating condition-specific retention rates, providing important information for design and recruitment for the future R01 study. Based on our prior study of adolescent smoking cessation, estimated intra-school correlation=0.01, for a design effect due to within-school clustering of $1 + [0.01 \times (20 - 1)] = 1.19$, and an effective sample size per condition of $40/1.19 = 34$. Based on our prior studies in

adolescents in school settings, we anticipate at least 85% retention. Thus, a conservatively wide 95% exact CI for per-condition retention rate is (68.9%, 95.0%).

Aim 2B (Monitor V2V Engagement and Assess Program Satisfaction) As the trial progresses, we will monitor engagement overall and by participant subgroups (e.g. by gender, race, age) as a formative assessment. Then, as the trial ends, we will also use this information as a component of our summative evaluation. We anticipate that engagement will lead to positive changes in acceptability, and satisfaction, and cessation.

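### The Aim 2B engagement analyses are read causally but carry no baseline covariate, so readiness to quit at entry could produce a positive association when engagement has no effect

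*Combined protocol and SAP*

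**What the plan says.** Section 13, Aim 2B, states the expectation in causal terms: "We anticipate that engagement will lead to positive changes in acceptability, and satisfaction, and cessation". The subsection on defining engagement level then splits three components (assessments completed, videos viewed, messages to the coach) into higher and lower, and adds them: "The range for the summary score would be from 0 to 3".

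Two analyses of this score follow. For satisfaction (CSQ-8): "We will assess the association of this score with the acceptability and satisfaction score using linear mixed modeling". For cessation: "Similarly, we will look for association between summary score and cessation", with no model named. Neither lists a covariate. The plan says the team could look at "predictors of engagement (by the adolescent's characteristics", but does not carry those characteristics into the outcome models. It acknowledges limited power and says the results are to guide a later grant application.

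Table 2 in Section 11 marks the engagement measure "Engagement (V2V only", so these comparisons lie inside one arm. The same table collects "Stage of change: Prochaska's Stages of Change" at baseline and six months, along with self-efficacy (SEQ-12), nicotine dependence (HONC) and recent use.

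Eligibility in Section 6 sets no condition on motivation to quit: "Current e-cigarette use is defined as a response greater than “0 days” to the question" about the past 90 days. Section 5 says that V2V is intended both for adolescents not yet ready to quit and for those who are.

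**The concern.** Schools are randomised, but the level of engagement within V2V is not; each student sets it. An association between the score and an outcome can arise because engagement helps, or because students who were readier to quit at entry both used the tools more and were more satisfied or more likely to stop. The planned models cannot separate the two explanations. Because the trial deliberately enrols students across the range of readiness, this confounder will vary in the sample.

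At stake is what the next study takes from this one. A positive result could credit V2V components with what students brought with them. The plan's caveat about power concerns imprecision. It does not warn that the estimate may be biased.

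**Working it through.** **The plan's own figure.** The only sample-size calculation is for retention. Design effect = 1 + 0.01 × (20 − 1) = 1.19; 40 / 1.19 = 33.6, rounded to 34. The exact 95% interval for 29/34 is 68.9% to 95.0%, as stated. No figure is given for the engagement analyses.

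**Inputs**
- Students analysed: 0.85 × 40 = 34 V2V completers (Section 25).
- Score: three components, each split at its median and summed to 0–3 (Section 13; for coaching messages the plan also allows another quantile).
- Assumed, not in the documents: two-sided 5% level; correlation r of baseline readiness z with each engagement component and with CSQ-8; odds ratio (OR) of quitting per SD of z; quit rate at average readiness of 15% or 20%.
- Engagement has no effect on either outcome.
- School clustering is left out, since the plan's intra-school correlation is 0.01.

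**CSQ-8, closed form.** Let S be the score and Y the standardised CSQ-8 value.
- Cov(S, z) = 3 × r × 0.3989
- Var(S) = 0.75 + 6 × arcsin(r²) / (2π)
- Spurious slope = r × Cov(S, z) / Var(S)
- Corr(S, Y) = slope × √Var(S)
- Rejection rate ≈ Φ(k − 1.96) + Φ(−k − 1.96), where k = atanh(Corr) × √(34 − 3)

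| r | Cov(S, z) | Var(S) | Slope (SD per point) | Corr | k | Rejection |
|---|---|---|---|---|---|---|
| 0.3 | 0.359 | 0.836 | 0.13 | 0.118 | 0.66 | 10% |
| 0.4 | 0.479 | 0.903 | 0.21 | 0.201 | 1.14 | 21% |
| 0.5 | 0.598 | 0.991 | 0.30 | 0.301 | 1.73 | 41% |

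Simulation of the same set-up agrees: about 10–11%, 20–22% and 40–42%. With r = 0 it gives about 5%.

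**Cessation, simulation** (logistic likelihood-ratio test, 34 students, no covariate).

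| r | OR per SD | Quit rate at average readiness | Rejection |
|---|---|---|---|
| 0 | 1 | 15% / 20% | 6.5% / 6.0% |
| 0.3 | 1.5 | 20% | 7.9% |
| 0.4 | 2 | 15% | 11.3% |
| 0.5 | 2 | 20% | 15.6% |
| 0.5 | 3 | 15% / 20% | 24.9% / 28.9% |

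The test is slightly liberal at this size, so the reference is about 6%, not 5%. In the r = 0.5, OR 2 setting the spurious odds ratio is about 1.5 per score point.

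**Effect of adjustment.** Adding a four-level stage-of-change covariate brings CSQ-8 rejection to 5–6% and cessation to 6–7%, but only if the item captures readiness without error and readiness is the sole confounder. If the item has reliability 0.7 or 0.5, adjusted CSQ-8 rejection is about 8% or 10% at r = 0.4 and about 12% or 19% at r = 0.5. The standard error of the engagement coefficient rises by about 2% to 16%.

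**The case against.** The strongest reply is that these analyses are exploratory. Aim 2B has no numbered hypothesis; only H1 (Aim 2A) and H2 (Aim 2C) exist. The analysis sentences speak of association, and no significance level or decision rule is attached. A reader might infer from the anticipation sentence that Aim 2B is a formal causal test. The documents do not support that: the causal reading rests on one sentence of expectation. Even so, that sentence is the only interpretation offered, and nothing beside it warns of selection.

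A reader might also infer that the plan never controls for confounding of engagement. That goes too far. Under Aim 2C, Section 13 lists engagement among possible mediators, plans to control for confounders of the mediator–outcome link, and asks for caution in interpreting the results. This shows that the principle is accepted, but it does not repair Aim 2B: the confounders are not named, satisfaction is not covered, and engagement is recorded only in V2V, so a between-arm mediation model for it is not defined.

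The size is also open to challenge. Every correlation and odds ratio is assumed. A readiness–satisfaction correlation of 0.4 to 0.5 is hard to support from the documents, because CSQ-8 rates the program and not quitting. At r = 0.3 the excess is modest. This stands, and is why a range is given. A school term in the mixed model would not help, since the confounding is between students.

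**Conclusion.** The point holds for Aim 2B. The two engagement models, as written, can return a positive association that reflects readiness at entry, while the text invites a causal reading. With 34 students, no true effect and an assumed two-sided 5% level, CSQ-8 false positives are about 10% to 42% for assumed correlations of 0.3 to 0.5. For cessation they run from about 8% to 25% for correlations of 0.3 to 0.5 and odds ratios of 1.5 to 3 per SD; the top figure is 29% if 20% rather than 15% quit at average readiness. If readiness is only weakly related to engagement and outcome, the problem is small.

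A reader might infer that adjusting for stage of change would settle the causal question. It would not: with an imperfect item, CSQ-8 rejection stays at roughly 8% to 19% for correlations of 0.4 to 0.5, and other confounders may remain. This is an inexpensive improvement to a secondary analysis. It does not touch the primary feasibility outcome, H1 or the between-arm estimates under H2.

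**What to change.** In Section 13, under the definition of engagement level, add baseline stage of change as a covariate in both the CSQ-8 and the cessation model. Report the adjusted estimate and its interval beside the unadjusted one. In the Aim 2B paragraph, replace the wording that engagement produces better outcomes with a statement that it is expected to be associated with them, and add that measured covariates do not remove all confounding.

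Optional: further baseline covariates for CSQ-8 (past-30-day use, HONC), and penalised (Firth) logistic regression for cessation if quitters are few.

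The cost is a wording change and one covariate already collected. It uses one degree of freedom if stage is scored as ordered, or three as four categories, and widens the interval slightly (standard error about 2% to 16% larger in the settings examined). No new data, visits or participants are needed.
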